8.3.1.2. Serious adverse events

Any adverse event that at, any dose:

- results in death,
- is life-threatening⁽¹⁾,
- requires inpatient hospitalization or prolongation of existing hospitalization,
- is medically significant⁽²⁾,
- results in persistent or significant disability/incapacity⁽³⁾,
- is a congenital anomaly/birth defect⁽⁴⁾.

⁽¹⁾ Life-threatening in this context refers to an event in which the participant was at risk of death at the time of the event; it does not refer to an event which hypothetically might have caused death if it was more severe.

⁽²⁾ Any event that might not be immediately life-threatening or result in death or hospitalisation, but might jeopardise the participant or might require intervention to prevent one of these outcomes (for example: oedema or allergic bronchospasm that required intensive treatment at home, blood dyscrasias, convulsions that do not result in hospitalisation, or development of drug dependence or drug abuse). The investigator should exercise his/her scientific and medical judgement to decide whether or not such an event requires expedited reporting to the sponsor.

⁽³⁾ Disability/incapacity in this context refers to any event that seriously disrupts the ability of the participant to lead a normal life, in other words leads to a persistent or permanent significant change, deterioration, injury or perturbation of the participant's body functions or structure, physical activity and/or quality of life.

⁽⁴⁾ Congenital anomaly or birth defect refers to the exposure to the IMP before conception (in men or women) or during pregnancy that resulted in an adverse outcome in the child.

8.3.1.3. Adverse events of special interest

Not applicable.

8.3.1.4. Overdose

This refers to any intake of a quantity of IMP which is above the maximum dose recommended in the study protocol, independently of the occurrence of any adverse event.

The quantity should be considered per administration or cumulatively regarding the maximum dose recommended in the study protocol. For instance, as the study protocol requires two daily administrations, one intake of the planned two daily intakes at the same time should be considered as overdose.

8.3.1.5. Events requiring an immediate notification (ERIN)

An event must be **notified immediately** (i.e. **within 24 hours**) to the sponsor if it is:

- a serious adverse event,
- an overdose of the IMP even if asymptomatic,
- any intake of the IMP by a person around the participant,
- a pregnancy.

8.3.2. Responsibilities of the investigator

For any adverse event and special situation mentioned above the investigator must:

- **Note in the participant's medical file** the date on which he/she learned of the event (at a follow-up visit or a telephone contact with the participant or a third person, ...) and any other relevant information which he/she has learned of the event,
- **Report the event to the sponsor** using the AE form (in case of ERIN, the reporting should be done immediately),
- Evaluate the seriousness, intensity and causality,
- **Document** the event with additional useful information,
- Ensure the **follow-up** of the event,
- **Fulfil his/her regulatory obligations** to the Competent Authorities and/or to the IRB/IEC, in accordance with local regulations.

[figure not shown]
8.3.2.1. Time frame for AE reporting

Any event meeting the above mentioned definitions (see [section 8.3.1](#)) must be reported to the sponsor on an adverse event form if it occurred:

- before the first intake of the test drug, **for event associated with any procedure/condition required by the study protocol**: procedure (duplex ultrasonography, ECG, etc.), change or withdrawal of previous/concomitant treatment relating to the conditions of the protocol.
- at any time after the first intake of the test drug up to the participant's last study visit for all events,
- after the participant's last study visit:
 - up to 30 calendar days after the participant's last study visit for all ERIN, regardless of the supposed role of the research (IMP, or experimental procedure).
 - irrespective of the time of onset after the end of the study in case of serious adverse event related to the research (IMP, or experimental procedure).

Of note, events occurring between the signature of the informed consent and the first administration of the test drug for which the investigator does not consider an association with

any procedure/condition required by the study protocol must be reported as medical history in the dedicated form of the e-CRF.

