4.2. Experimental design

4.2.1. Study plan

This is a phase IIa, prospective, international, multicentre, randomised, double-blind, placebo-controlled, parallel group, dose-finding study in patients with venous leg ulcer.

The study will consist of 3 periods as follows:

- A selection period of 14 days of placebo treatment in which participants will be investigated for documenting the presence of Chronic Venous Disease and assessment of type and size of Reference Leg Ulcer. Their clinical and biological status will be documented prior to inclusion. From the selection visit, standard of care will be changed to standardized compression and local wound care with sterile saline solution or sterile water and “non active” dressings.
- A double-blind controlled period of 42 days: 6 weeks of treatment with one dose of S42909 or placebo on top of standardized compression and wound local care.
- A follow-up period of 2 weeks with standard of care only after the last dose of S42909 (from W006 to W008).

An Interactive Web Response System (IWRS) will be set up for participant selection/inclusion randomisation and allocations of the therapeutic units pack numbers.

About 250 patients suffering from chronic venous disease and having at least one active venous ulcer matching with the selection criteria (CEAP classification C6 stage) will be selected at the selection visit (ASSE) to include 204 participants at W000 visit.

During the ASSE visit, the underlying chronic venous disease will be documented and recorded in the participant medical file according to CEAP classification. To document the chronic venous disease, a duplex ultrasonography should have been performed within the previous 6 months or will have to be performed during ASSE or the placebo selection period

of 14 days to have the results before inclusion and allow verification of compliance with the inclusion criteria. If data of the duplex ultrasonography report performed in the previous 6 months doesn't permit to fill in the e-CRF and/or to rule out an acute venous thrombosis, a duplex ultrasonography must be performed before inclusion. The presence of a peripheral arterial component of the disease must be ruled out by measuring and calculating the ankle-brachial pressure index (ABPI) ideally by continuous waves Doppler, otherwise by duplex ultrasonography (see [Appendix 5](#)) before applying high level compression ([Mosti, 2009](#)).

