- If complete healing of all ulcers (including the reference ulcer) is observed, the participant will keep the same standardized compression until the end of the study or be switched to a compression for leg ulcer recurrence prevention (> 18 mmHg) if the participant refuses (this type of compression will not be provided to the sites). The participant will continue to take the study drug until W006.

The end-of-study visit is scheduled to take place at W008 or, in case of prematurely withdrawn participants as soon as possible, after stopping the use of standardized compression, or after the last IMP intake. In case of premature withdrawal, the next expected visit will be performed. If the next expected visit is W003, biochemistry and haematology should be added to the assessments to be performed during this visit.

An electronic case report form (e-CRF) will be used for data capture during the study.

[figure not shown]
The study plan is shown in [Figure \(4.2.1\) 1.](#)

Figure (4.2.1) 1 - Study plan**- Treatment periods-**

Placebo	Group A	S42909 dose 100 mg, p.o., 50 mg bid	N=34
	Group B	S42909 dose 200 mg, p.o., 100 mg bid	N=34
	Group C	S42909 dose 400 mg, p.o., 200mg bid	N=34
	Group D	S42909 dose 800 mg, p.o., 400 mg bid	N=34
	Group E	S42909 dose 1200mg, p.o., 600mg bid	N=34
	Group F	Placebo, p.o., bid	N=34

← On top of standard of care (standardized compression and local wound care)

Study periods

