13. Participant willing to use highly effective contraceptive measures adequate to prevent the participant or the participant's partner from becoming pregnant (i.e. not menopausal, non-hysterectomised, non-surgically sterilised women) throughout the study and for 3 months after completion of study treatment. Highly effective methods of birth control refer to those which result in a low failure rate (i.e. less than 1% per year), when used consistently and correctly, such as combined hormonal contraception associated with inhibition of ovulation (oral, intravaginal, transdermal), progestogen-only hormonal contraception associated with inhibition of ovulation (oral, injectable, implantable), some intra uterine devices (IUDs), intrauterine hormone-releasing system (IUS), true sexual abstinence (when this is in line with the preferred and usual lifestyle of the participant). The investigator must inform the participants about the risks of not using an effective method of birth control during the course of the study.
 - Non menopausal woman means that the time since last menstrual period is < 1 year, in a woman of appropriate age.
 - Surgically sterilised is defined as having had a bilateral tubal ligation, hysterectomy or bilateral oophorectomy.

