The TU box allocated at W004 visit will be retrieved from the participant and the drug accountability of the remaining tablets will be performed.

The IMP treatment will be stopped at this visit with the morning dose taken after PK predose at site and the participant will enter the follow-up period where he/she will continue wearing the compression stockings until the end of the study. The measurements of the participant's leg will be checked at this visit and if the stocking size has changed, 1 new stocking kit will be provided to the participant according to the leg measurement chart.

For each participant, the IMP will only be dispensed during the study. At the last visit of the study, the investigator will propose a treatment adapted to the nature of the clinical state of the participant.

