8.3.2.4. Follow-up of adverse events

The investigator must ensure that follow-up of the participant is appropriate to the nature of the event, and that it continues until resolution if deemed necessary.

Any change in terms of diagnosis, intensity, seriousness, measures taken, causality or outcome regarding an adverse event already reported must be written up in a new complete evaluation of the event documented on the “Adverse event” page previously created for the event in the e-CRF.

If the adverse event has not resolved at the participant's final visit in the study, the participant must be followed up suitably and any information on the outcome of the event will be noted on the « Adverse Event » page previously created for the event in the e-CRF.

If the follow-up of the participant is not done by the investigator him/herself (hospitalisation, followed by a specialist or the participant's general practitioner, etc.), the investigator will do everything to establish/maintain contact with the person/department in charge of follow-up of the participant.

8.3.2.5. Special situations (pregnancy, overdoses, intake of IMP by a person around the participant)

Pregnancy

If a female participant in the study becomes pregnant, the investigator must:

- stop immediately the IMP,
- report it on an « Adverse Event » page as well as on the specific paper pregnancy form to be notified immediately (ERIN),
- contribute to the follow-up of this pregnancy and provide the sponsor with information concerning this follow-up
- If the partner of a participant becomes pregnant during the course of the study or within 3 months after completion of study treatment, the pregnancy should not be reported in the e-CRF. The investigator should **immediately** contact the sponsor (contact details provided in the investigator's study file) who will inform him/her about the procedure to be followed.

Overdose of IMP

- In case of overdose, the investigator should report it on an “Adverse Event” page to be notified immediately (ERIN).
- Overdose should be followed-up to ensure that the information is as complete as possible with regards to:

- dose details (number of units, duration,...) and, if multiple overdose, details regarding other medicinal products or substance ,
- context of occurrence, i.e. intentional (suicide attempt, other reason) or accidental (error in prescription, administration, dispensing, dosage),

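### A female participant's pregnancy is reportable only to 30 days after her last visit, while contraception and partner-pregnancy reporting run to 3 months after treatment

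*Protocol*

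**What the plan says.** Four provisions of the protocol bear on this point.

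- **Status of pregnancy.** Section 8.3.1.5 lists pregnancy among the ERINs, to be notified within 24 hours.
- **Collection period.** Section 8.3.2.1 requires reporting of events that occur after the last visit "up to 30 calendar days after the participant's last study visit for all ERIN". The only open-ended clause there is for serious adverse events related to the research.
- **Contraception.** Criterion 13 in section 5.1.2 requires highly effective contraception "throughout the study and for 3 months after completion of study treatment".
- **Special situations.** Section 8.3.2.5 treats the two kinds of pregnancy differently. For the participant: "If a female participant in the study becomes pregnant, the investigator must" stop the IMP, report the pregnancy as an ERIN and help follow it up. No period after the study is given. For a partner: "If the partner of a participant becomes pregnant during the course of the study or within 3 months after completion of study treatment", the investigator must contact the sponsor at once.

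On timing, section 6.2 says of W006: "The IMP treatment will be stopped at this visit with the morning dose taken after PK predose at site". The last visit, W008, follows two weeks later, and section 6.1 gives that interval as 14 days with a tolerance of 4. The last scheduled pregnancy test is at W008 (section 8.2). The SAP does not address pregnancy reporting.

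**The concern.** The protocol applies 3 months after treatment to contraception and to pregnancy in a partner, but not to pregnancy in the woman who took the drug. Her paragraph in 8.3.2.5 sets no limit of its own, so the general ERIN limit in 8.3.2.1 governs.

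The result is an inversion. Suppose a pregnancy begins 60 days after the last dose. If it is in a participant's partner, the sponsor must be told immediately. If it is in a female participant who completed the trial, nothing in the protocol requires a report. The sponsor could then miss the pregnancy and never start the follow-up that 8.3.2.5 describes. For an unlicensed drug, this is information the sponsor would want, and the protocol already arranges to collect it for the less directly exposed group.

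**Working it through.** The plan gives no figure of its own here, so the check is calendar arithmetic.

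**Inputs**

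- Reporting limit: 30 days after the last visit (8.3.2.1).
- Completer: last dose on the morning of W006 (6.2); W008 is 14 ± 4 days later, so 10 to 18 days (6.1).
- Early stopper: two sections govern the final visit. Section 4.2.1 places it "in case of prematurely withdrawn participants as soon as possible, after stopping the use of standardized compression, or after the last IMP intake" and also asks for the next scheduled visit to be held. Section 5.6.2 lets it fall either at discontinuation or at the date the study would have ended for her. That date is nominally day 42 + 14 = 56.
- Three months: taken as 91 days (assumption; 90 to 92 is the plausible range).

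**Formulas**

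Days covered = (last dose to last visit) + 30. Days uncovered = 91 − days covered. Share = days uncovered / 91.

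| Case | Last dose to last visit | Days covered | Days uncovered | Share |
|---|---|---|---|---|
| Completer, W008 four days early | 10 | 40 | 51 | 56% |
| Completer, W008 on schedule | 14 | 44 | 47 | 52% |
| Completer, W008 four days late | 18 | 48 | 43 | 47% |
| Early stop, final visit on day of last dose | 0 | 30 | 61 | 67% |
| Early stop, final visit 7 days later | 7 | 37 | 54 | 59% |
| Stop at W004 (day 28), final visit day 56 | 28 | 58 | 33 | 36% |
| Stop at W001 (day 7), final visit day 56 | 49 | 79 | 12 | 13% |

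**Sensitivity**

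- *Length of 3 months.* For the on-schedule completer, 90 days gives (90 − 44)/90 = 51% and 92 days gives (92 − 44)/92 = 52%.
- *Denominator.* If the 42 treatment days are counted in the window, the on-schedule completer's share is 47/(91 + 42) = 35%.
- *Early stoppers.* The 13% is not a strict minimum: stopping before W001 and returning at day 56 would leave still less uncovered.

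If the woman's reporting period matched the partner period, the uncovered part would be zero in every row.

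**The case against.** The case on the other side has five parts.

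1. **Early stoppers.** A reader might infer that the gap is always widest for women who stop treatment early, because their last visit comes soonest. The documents do not support that as a rule. Section 5.6.2 allows the final visit at the planned end of study, and section 4.2.1 calls for the next scheduled visit. A woman who stops at W001 or W004 and returns at day 56 is better covered than a completer. The 67% is a worst case.

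2. **What is lost.** A reader might also infer that all later pregnancy outcomes go uncollected. They do not. Section 8.3.1.2 counts a congenital anomaly as serious, and any related serious event is reportable without time limit. Section 8.3.2.1 also turns on when an event occurred, so a pregnancy that began inside the 30 days but was recognised later can be read as reportable. These points narrow the gap but do not close it. Pregnancy is not itself on the serious-event list, and a birth defect would be known late, and reportable only if judged related.

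3. **Exposure.** The protocol does not call the 3 months a risk period. SAP sections 3.1.2 and 3.6.1 use 15 days after the last intake, based on half-life, and protocol section 2 reports no accumulation of parent drug. Even the shortest coverage, 30 days, exceeds 15. This weakens any claim of continuing exposure in the uncovered weeks. It does not explain why partners are followed for longer than the women treated.

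4. **Denominator.** Contraception runs through the study as well as after it. With the treatment weeks counted, the completer's uncovered share is about 35%, so saying that about half is uncovered is right only for the 3 months after treatment.

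5. **Frequency.** Section 2 puts peak leg-ulcer prevalence between 60 and 80 years of age, so few women will be affected. That stands, and it limits the weight of the point.

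**Conclusion.** The inconsistency is real and lies wholly within the protocol. As written, a female participant's pregnancy is reportable over a shorter period than a partner's. For completers, reporting stops 40 to 48 days after the last dose, which leaves 43 to 51 of about 91 post-treatment days (47% to 56%) uncovered. For early stoppers the worked cases run from about 13% to about 67%, and the timing of the final visit decides where a given woman falls.

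These figures rest on three readings: that 3 months is about 91 days, that only post-treatment time is counted, and that the 8.3.2.1 limit governs because the female-participant paragraph sets none.

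The expected number of events is small, although the documents do not give the number of women of child-bearing potential. No efficacy or planned statistical conclusion depends on this. It is a gap in safety reporting that should be closed because the wording is easy to align.

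**What to change.** Reconcile criterion 13, section 8.3.2.1 and section 8.3.2.5. In 8.3.2.1, and again in the female-participant paragraph of 8.3.2.5, state that pregnancy in a female participant is reportable as an ERIN over the same post-treatment period the protocol already uses for a partner's pregnancy. If the sponsor considers a shorter period sufficient, the sections still disagree and the reason for the difference should be stated. The change concerns data collection only and alters no dose, contraception or treatment rule.

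No extra scheduled contact is needed. Partner reporting has none, so adding a telephone call for women would go beyond making the sections agree.

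The cost is two sentences of text, the amendment procedure of section 17.1.2 if the change is classed as substantial, and slightly longer passive reporting for a small subgroup. By the SAP date (2 March 2020) the number included was final at 121, so in this trial the change helps only women still within the post-treatment period. Otherwise it is a correction to carry into any later protocol that reuses this text.

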8.3.2.2. Evaluation of seriousness, intensity and causality

It is important that the investigator gives his/her own opinion regarding the **seriousness**, the **intensity** of the event as well as the **cause-effect relationship** between an adverse event and the IMP. This evaluation must be assessed by the investigator and reported in the AE form.

The Seriousness should be evaluated according to international guidances (see definition section 8.3.1.2, in accordance with ICH Topic E2A and Directive 2001/20/EC of the European Parliament and of The Council of 4 April and (<http://www.fda.gov/downloads/drugs/guidancecomplianceregulatoryinformation/guidances/ucm071696.pdf>).

The Intensity should be evaluated according to the following rule:

- mild: signs or symptoms, easily tolerated, relieved with symptomatic treatment,
- moderate: enough discomfort to cause interference with usual activity, only partially relieved with symptomatic treatment,
- severe: incapacity in some regular activities, not easily relieved with symptomatic treatment.

The causal relationship to the IMP must be assessed when reporting the AE in the AE form. Only cases ticked "related" by the investigator or judged by the sponsor as having a reasonable suspected causal relationship to the test drug (AE linked to the mechanism of action of the test drug...) will be considered as suspected Adverse Drug Reaction. In general, the expression reasonable causal relationship means to convey that there is evidence or arguments to suggest a causal relationship.

8.3.2.3. Documentation of the event

The investigator must ensure that all events are well documented. In particular for ERIN, he/she should provide the sponsor, as they become available, with anonymized copies of the documents which provide additional useful information, such as hospital admission reports, reports of further consultations, laboratory test reports, reports of other examinations aiding diagnosis (where possible, the results from pre-test drug assessments should be appended for comparison with the results obtained under test drug), or the autopsy report, if autopsy is performed.

8.3.2.4. Follow-up of adverse events

The investigator must ensure that follow-up of the participant is appropriate to the nature of the event, and that it continues until resolution if deemed necessary.

Any change in terms of diagnosis, intensity, seriousness, measures taken, causality or outcome regarding an adverse event already reported must be written up in a new complete evaluation of the event documented on the “Adverse event” page previously created for the event in the e-CRF.

If the adverse event has not resolved at the participant's final visit in the study, the participant must be followed up suitably and any information on the outcome of the event will be noted on the « Adverse Event » page previously created for the event in the e-CRF.

If the follow-up of the participant is not done by the investigator him/herself (hospitalisation, followed by a specialist or the participant's general practitioner, etc.), the investigator will do everything to establish/maintain contact with the person/department in charge of follow-up of the participant.

8.3.2.5. Special situations (pregnancy, overdoses, intake of IMP by a person around the participant)

Pregnancy

If a female participant in the study becomes pregnant, the investigator must:

- stop immediately the IMP,
- report it on an « Adverse Event » page as well as on the specific paper pregnancy form to be notified immediately (ERIN),
- contribute to the follow-up of this pregnancy and provide the sponsor with information concerning this follow-up
- If the partner of a participant becomes pregnant during the course of the study or within 3 months after completion of study treatment, the pregnancy should not be reported in the e-CRF. The investigator should **immediately** contact the sponsor (contact details provided in the investigator's study file) who will inform him/her about the procedure to be followed.

Overdose of IMP

- In case of overdose, the investigator should report it on an “Adverse Event” page to be notified immediately (ERIN).
- Overdose should be followed-up to ensure that the information is as complete as possible with regards to:

- dose details (number of units, duration,...) and, if multiple overdose, details regarding other medicinal products or substance ,
- context of occurrence, i.e. intentional (suicide attempt, other reason) or accidental (error in prescription, administration, dispensing, dosage),
- related signs and symptoms ("No related adverse events" to be reported otherwise),
- outcome.

Intake of IMP by a person around the participant.

This event should not be reported in the e-CRF. The investigator should immediately contact the sponsor (contact details provided in the investigator's study file) who will inform him/her about the procedure to be followed.

